5.2.2 Replacement - amended

There will be no replacement of randomized patients who withdraw from the study or prematurely discontinue study medication⁴⁹.

⁴⁴ Per Amendment 4

⁴⁵ Per Amendment 4

⁴⁶ Per Amendment 4

⁴⁷ Per Amendment 4

⁴⁸ Per Amendment 4

⁴⁹ Per Amendment 4

5.3 Patient identification

After a patient signs the informed consent form, the patient identification number for each patient will be provided to the investigators via IxRS. Patients will be identified by a unique 9-digit number consisting of the following:

- First 2 digits = Unique country code
- Next 3 digits = Unique study center number within the country
- Last 4 digits = Unique current patient number within the study center of a given country; sequential number reflecting the order in which the patients signed the informed consent form at the center (4 digits)

Patient identification numbers must be used in sequence and no number should be skipped, substituted, or reused.

6. Treatment

6.1 Treatments to be administered

Test drug:	Riociguat
Dosage:	0.5 mg, 1 mg, 1.5 mg, 2 mg, and 2.5 mg (dose titration)
Route of administration:	Oral
Time and frequency of administration:	TID

The optimal dose should be determined during the initial 10-week dose titration period based on monitoring of the patient's SBP and well-being.

The recommended starting dose is 0.5 mg TID. The intervals between drug intake should be 6–8 hours. The dosage should be increased by 0.5 mg increments no sooner than 2 weeks apart to 1 mg, 1.5 mg, 2 mg, and 2.5 mg TID, resulting in a maximum total daily dose of 7.5 mg. Patients should be maintained on lower doses if higher doses are not tolerated (minimum dose of 0.5 mg TID, see Section 5.2.1). After the dose titration period, riociguat should be continued at the optimal dose for the duration of the maintenance period.

6.2 Identity of study treatment

Riociguat

Riociguat is supplied in various strengths as film-coated, immediate-release tablets (see [Table 6–1](#)). Riociguat and placebo tablets will have similar appearance at all dose strengths.

All study drugs will be labelled according to the requirements of local law and legislation. Label text will be approved according to the sponsor's agreed procedures, and a copy of the labels will be made available to the study site upon request.

For all study drugs, a system of numbering in accordance with all requirements of Good Manufacturing Practice (GMP) will be used, ensuring that each dose of study drug can be traced back to the respective bulk ware of the ingredients. Lists linking all numbering levels will be maintained by the sponsor's clinical supplies Quality Assurance group.

A complete record of batch numbers and expiry dates of all study treatment, as well as the labels, will be maintained in the sponsor study file.

Table 6–1 Identity of investigational product

International non-proprietary name (INN)	Riociguat
Sponsor's internal reference number	BAY 63-2521
Formulation	Film-coated tablets
Galenical form	Round immediate-release tablets, diameter 6 mm
Composition	Active ingredient: Methyl 4,6-diamino-2-[1-(2-fluorobenzyl)-1H-pyrazolo [3,4 b]pyridine-3-yl]-5-pyrimidinyl (methyl)carbamate Empirical formula: C ₂₀ H ₁₉ FN ₈ O ₂ Molar mass: 422.42 g/mol (molarity) Excipients: lactose, microcrystalline cellulose, magnesium stearate, crospovidone* , hypromellose* , and sodium lauryl sulphate* Coating: hydroxypropyl cellulose, hypromellose, propylene glycol, iron oxide (red and yellow), and titanium dioxide.
Strength	0.5 mg, 1 mg, 1.5 mg, 2 mg, 2.5 mg
Material numbers	83296470 BAY 63-2521 TABL 0.5 mg 511 COAT 83296535 BAY 63-2521 TABL 1 mg 512 COAT 83296543 BAY 63-2521 TABL 1.5 mg 513 COAT 83296578 BAY 63-2521 TABL 2 mg 504 COAT 83296608 BAY 63-2521 TABL 2.5 mg 515 COAT
Packaging	High-density polyethylene (HDPE) bottles

Abbreviation: TABL = tablet

*Not in placebo tablets

Matching placebo

Matching placebo tablets will appear identical to active riociguat tablets but will not contain active study drug product (riociguat) or any of the excipients marked with an asterisk as outlined in [Table 6–1](#).

Storage requirements

All investigational drugs used during the trial will be stored at the investigational sites at room temperature in a place inaccessible to unauthorized personnel, ie, in a locked cabinet.

No special storage conditions are required.

6.3 Treatment assignment

This is a randomized, double-blind, placebo-controlled, parallel-group, multinational, multicenter study. Patients who complete all screening procedures and meet all eligibility criteria are to be randomized via IxRS in a 1:1 ratio to receive either riociguat or placebo.

The patient randomization scheme will use permuted blocks sized as a multiple of 2. Each block will be allocated to a country or group of nearby countries within a region. No other stratification is planned.

An IxRS site manual will be provided to the investigative centers.

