8.4.2 Efficacy - amended

In the efficacy analyses, countries and centers will be clustered by geographic region. The decision on country pooling will be made before unblinding. Statistical analyses will be adjusted for these countries / geographic regions.

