8.4.2.1 Primary endpoint¹²¹

The primary analysis will be the change in mRSS from baseline to all assessments post baseline up to Week 52 using mixed model repeated measures (MMRM) with baseline mRSS as a covariate, fixed effects treatment arm and region, the interaction effect between study visit and treatment arm, and patient specific random effects to account for both heterogeneity among patients and correlation among measurements taken on the same patient with an unstructured covariance assumption. The main estimand of interest is the treatment difference

¹²⁰ Per Amendment 1

¹²¹ Per Amendment 4

between the riociguat and placebo treatment arms at Week 52. The null hypothesis to be tested is no difference between riociguat and placebo at this visit.

The model statement is:

$$Y_{ij} = \mu + \beta X_i + t_k + r_l + v_j + (tv)_{jk} + s_i + \varepsilon_{ij}$$

where Y_{ij} is the change from baseline in mRSS to visit j for subject i that is in treatment group k and region l ; μ is the intercept, β is the baseline covariate effect, X_i is the baseline mRSS for subject i , t_k is the fixed effect of treatment k , r_l is the fixed effect of region l , v_j is the fixed effect of visit j , $(tv)_{jk}$ is the interaction effect of treatment k by visit j , s_i is the random effect of subject i and $\varepsilon_{ij} \sim \text{Normal}(0, \sigma^2)$ represents the residual variance component with $\text{corr}(\varepsilon_{ij}, \varepsilon_{ij'}) = \rho_{jj'}$, $j \neq j'$

As a sensitivity analysis, the MMRM using the above model will also be applied to assessments post-baseline up to termination of study medication or initiation of rescue medication. In addition, the MMRM on all assessments will be repeated including additional effects time on rescue medication and time on study medication. MMRM assumes missing at random; mRSS by time of patient discontinuation from study medication¹²² will be summarized and further methods using multiple imputation that allow for missing data not at random will be investigated. Details of such methods will be described in the SAP.

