8.6 Determination of sample size - amended

There is lack of positive trials in dcSSc. Most trials have used change in mRSS to Month 6 or Month 12 as the primary endpoint, and 4 published articles are referenced for the estimate of variability in this study (Table 8-1).

¹³³ Per Amendment 6

¹³⁴ Per Amendment 5

¹³⁵ Per Amendment 5

Table 8–1 References for estimate of variability

Reference	Trial treatment	Active arm SD	Placebo arm SD
Postlethwaite (2008)[35]	Collagen 0 – 12 months	7.6	7.7
Khanna (2009)[26]	Relaxin 0 – 24 weeks	7.0	7.0
Merkel (2012)[36]	0 – 6 month meta-analysis		7.2
	0 – 12 month meta-analysis		8.4
Amjadi (2009)[37]	D-Pen		8.6
	Relaxin		7.0
	Collagen		7.1

Abbreviations: D-Pen = D-penicillamine; SD = standard deviation.

Taking these sources into account, a reasonable upper bound for the estimate of the standard deviation to be used in the sample size calculation of this study has been taken as 8.0.

One of the components of exploratory efficacy measure¹³⁶ mRSS progression is a 5 point or more deterioration from baseline to any assessment in the 12 month study period, this being considered a clinically meaningful change [14]. For the primary sample size calculation based on change in mRSS from baseline to Week 52, a slightly more conservative 4-point difference between riociguat and placebo has been taken, given that the trials referenced above never achieved a 5-point, or even a 4-point, superiority of active over placebo.

The primary efficacy estimand in this study will be change in mRSS from baseline to Week 52. Assuming a standard deviation of 8 points, a power of between 70% and 80% and a two-sided significance level of 5%, with a 1:1 randomization, then to detect a placebo-adjusted difference of 4 points, between 51 and 64 patients in each treatment group, a total of 102 to 128 patients, would be required to be valid for the ITT analysis (see Table 8–2). Allowing for up to two patients randomized and not treated, approximately 130 randomized patients are planned.¹³⁷

Table 8–2 Power calculations: power varying from 70% to 80% in 2% stages¹³⁸

N per group	51	53	56	58	61	64
Total N	102	106	112	116	122	128
Power (%)	70	72	74	76	78	80

N = number of patients

Sources of these sample size and power calculations are nQuery version 7.0, module MTT0-1.¹³⁹

¹³⁶ Per Amendment 4

¹³⁷ Per Amendment 5

¹³⁸ Per Amendment 5

¹³⁹ Per Amendment 5

9. Data handling and quality assurance

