4.5.3 Definition of regions

The following regions are used for further subgroup analyses:

- Europe and Australia/New Zealand: Belgium, Netherlands, Switzerland, Germany, Czech Republic, Hungary, Turkey, Spain, Italy, France, UK, Australia, and New Zealand
- North America: US and Canada
- East Asia: Japan.

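### Randomization is blocked by country group, but the primary and stratified analyses adjust only for region; if region is coarser, the primary test may be mildly conservative

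*Protocol*

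**What the plan says.** **Randomization.** Protocol 6.3 specifies permuted blocks and 1:1 allocation. On where the blocks sit it says "Each block will be allocated to a country or group of nearby countries within a region", and it plans no further stratification. On this wording a region contains one or more blocking units.

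**Analysis.** Protocol 8.4.2 says "In the efficacy analyses, countries and centers will be clustered by geographic region". Pooling is to be settled before unblinding. The sentence on adjustment names countries and geographic regions as alternatives without choosing between them. Section 8.4.2.1 specifies the primary MMRM "with baseline mRSS as a covariate, fixed effects treatment arm and region", and its model equation has a region term and no country term. The ANCOVA in the same section also uses region, and the Wilcoxon test is stratified by region. Section 8.4.2.2 stratifies the Mantel-Haenszel analyses by region, including CRISS, the first test in the secondary hierarchy.

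**Region definition.** The only list is in SAP 4.5.3, which covers the extension phase and introduces its regions for subgroup analyses. It has three levels. The first begins "Europe and Australia/New Zealand: Belgium, Netherlands, Switzerland, Germany, Czech Republic" and goes on to make up eleven European countries (counting Turkey) plus Australia and New Zealand. The others are the US with Canada, and Japan. The SAP's introduction refers to a separate main-phase SAP, finalized before unblinding, which is not supplied.

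**The concern.** Blocking within a country group makes the arms nearly equal in size there, so differences between groups in mean mRSS change largely cancel from the treatment contrast. A model that knows only the region leaves those differences in the residual. Its standard error then describes a noisier comparison than the one actually made, and the test rejects less often than its nominal level.

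The documents give some reason to expect such differences. From Week 26, rescue immunosuppressants are started at the investigator's discretion and are not provided by the sponsor (Protocol 6.9), and the primary analysis uses all assessments up to Week 52. Local prescribing can therefore reach the primary endpoint. At stake is a little power in a design that accepts 70% to 80% (Protocol 8.6).

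**Working it through.** **Inputs from Protocol 8.6.** SD 8; sample size set "to detect a placebo-adjusted difference of 4 points"; "a two-sided significance level of 5%, with a 1:1 randomization"; 64 per arm (128 in total) for 80% power.

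**The plan's own figure.** Two-sample t-test power with these inputs is 70.6, 72.2, 74.6, 76.1, 78.2 and 80.2% for 51, 53, 56, 58, 61 and 64 per arm. Table 8-2 states 70, 72, 74, 76, 78 and 80%, so it reproduces.

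**Assumed quantity.** Let ρ be the share of outcome variance lying between country groups within a region, with the total SD held at 8. The documents give no value, so a range is shown. The between-group SD is 8√ρ: 1.8, 2.5 and 3.6 mRSS points at ρ = 0.05, 0.10 and 0.20.

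**Closed form (upper bound).** This assumes perfect balance within groups and that region absorbs none of ρ.

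- Reported SE, region only: 8√(2/64) = 1.414.
- True SE: 8√((1−ρ)·2/64) = 1.378, 1.342 and 1.265 at ρ = 0.05, 0.10 and 0.20.
- Overstatement, 1/√(1−ρ) − 1: 2.6%, 5.4% and 11.8%.
- Power with region only, Φ((4 − t·1.414)/SE_true): 80.8%, 81.5% and 82.9%.
- Power with 8 country groups, Φ(4/SE_true − t): 82.2%, 84.2% and 88.1%.

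Here t is the 97.5% critical value on 128−1−3 = 124 degrees of freedom for region, and on 128−1−8 = 119 for 8 groups.

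**Simulation.** There were 10,000 trials per setting, with N = 128, blocks of 4, and 8 or 16 country groups of uneven size nested in three regions holding 60/28/12% of patients. There was a single Week 52 comparison, without baseline covariate or missing data. The number of groups, the block size and the region shares are also assumptions. Both models were fitted to the same data. Changes are in percentage points, taken before rounding.

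| ρ | Groups | Size, region only | Power, region only | Power, country groups | Change |
|---|---|---|---|---|---|
| 0 | 8 | 5.0% | 79.9% | 79.6% | −0.3 |
| 0 | 16 | 4.8% | 80.2% | 78.9% | −1.3 |
| 0.05 | 8 | 4.6% | 81.5% | 82.1% | +0.6 |
| 0.05 | 16 | 5.0% | 81.1% | 81.0% | −0.1 |
| 0.10 | 8 | 4.6% | 82.7% | 84.1% | +1.5 |
| 0.10 | 16 | 4.4% | 83.0% | 83.7% | +0.7 |
| 0.20 | 8 | 3.7% | 85.4% | 88.5% | +3.1 |
| 0.20 | 16 | 3.8% | 84.0% | 86.9% | +2.9 |

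With region only at ρ = 0.10, the mean reported SE was 1.383 (8 groups) and 1.388 (16 groups), against an empirical SD of the estimate of 1.338 and 1.351. The overstatement is 3.4% and 2.7%. At ρ = 0.20 it was 1.350 and 1.365 against 1.266 and 1.286, or 6.6% and 6.1%. The country-group model gave nearly the same empirical SDs: 1.338 and 1.367 at ρ = 0.10, and 1.261 and 1.291 at ρ = 0.20. The estimate is about equally precise either way; what differs is the standard error reported for it.

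**The case against.** **The mismatch is not established for the primary analysis.** The main-phase pooling is not in the supplied documents, Protocol 8.4.2 could be read as allowing country-level adjustment, and the three-region list serves descriptive extension-phase subgroups. If the main-phase regions equal the blocking groups, nothing is wrong. This stands as a limit on certainty. Against it, Protocol 6.3 places the blocking unit inside a region, the model equation carries region, and a level joining Europe with Australia and New Zealand cannot be a set of neighbouring countries. For Japan, region and country coincide, and for North America region and blocking group may do so.

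**Stronger readings go too far.** A reader might infer that the standard error ignores the randomization strata. It does not: region is a coarsening of them and is in the MMRM, the ANCOVA and the stratified tests. A reader might also infer that every endpoint in the hierarchy loses power. Only the primary endpoint has been calculated; CRISS is analysed as a binary outcome, and nothing here shows the effect on it or on the others.

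**The size rests on an undocumented variance.** This stands. At ρ = 0 the finer strata lose power, and at 0.05 they are about neutral. Rater differences are a weak source, because Protocol 7.6.6 has the same physician score a patient throughout and a constant offset cancels in a change score.

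**Coarser pooling can be a legitimate choice.** The 16 countries listed in SAP 4.5.3 would average 128/16 = 8 patients each. This is a fair reason for a merging rule, or for pooling that is openly justified.

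**Conclusion.** The point holds in a limited form. The text indicates that the analysis factor is coarser than the blocking factor, and nothing supplied says why. If country groups within a region differ in mean outcome, the primary test is conservative. With 10% to 20% of variance between groups, its size is about 4.5% to 3.7%, and about 1 to 3 points of power are forgone (up to about 5 in the closed form at 20%: 88.1 − 82.9 = 5.2). With little between-group variance there is nothing to gain, and the finer strata cost up to about 1 point.

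The treatment estimate is unbiased, and type I error stays at or below 5% within simulation error. The 80% planning figure is still met with region only, because it was computed from a total SD of 8 that already contains any between-country variation. These sizes depend on the assumed ρ, group structure and block size, and apply to a single-visit comparison of mRSS change.

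**What to change.** State the IxRS country groups to which blocks were allocated and how they map to region. Use those groups as the fixed effect in the MMRM and ANCOVA and as the stratum in the Mantel-Haenszel and stratified Wilcoxon analyses. Pre-specify, on blinded data, a rule that merges a sparse group with a neighbour in the same region. Keep region for subgroup display. If the coarser pooling is retained, give the reason.

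The rationale for Protocol Amendment 7 refers to main-phase results, so for this trial the change should now be reported as a labelled sensitivity analysis beside the pre-specified one.

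The cost is SAP wording, some small strata and a few degrees of freedom: 8 − 3 = 5 with 8 groups, and 16 − 3 = 13 if all 16 countries stood alone. If between-group variance is negligible, up to about 1 point of power is also lost.

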6.4 Dosage and administration

6.4.1 Selection of doses in the study - amended

Riociguat has been safe and well tolerated in previous clinical studies at multiple doses between 0.5 and 2.5 mg TID in patients with various forms of pulmonary hypertension, including PAH, CTEPH, and, in a small patient population, SSc-related pulmonary hypertension. The intervals between drug intake should be 6 to 8 hours⁵⁰.

Data from the phase III clinical program for riociguat in patients with pulmonary hypertension (PATENT and CHEST studies) showed that a starting dose of 1 mg TID was safe and effective. Because a few patients in both studies had their dosage reduced to 0.5 mg TID, the sponsor recognized that the 0.5 mg TID dosage may offer additional tolerability for some patients and adopted this additional dose recommendation. In the present study, the titration will start at 0.5 mg TID.

For further details refer to the IB.

6.5 Blinding - amended

Apart from the open-label extension period in the long-term extension phase, the study will be conducted in a double-blind fashion. Active riociguat and placebo tablet formulations will be identical in appearance (size, shape, color) and smell. The packaging and labeling will be designed to maintain blinded conditions for the investigator's team and the patients. The study data will remain blinded until database lock and authorization of data release according to standard operating procedures.

Appropriate measures will be taken to maintain blinding of the study team while PK and biomarker analysis is ongoing. Data with a potential to unblind (eg, plasma concentrations) are not to be handled by or shown to the study team members and will only be uploaded into the clinical database after official unblinding. The process of data flow will be documented separately (see also Section 7.4 and Section 7.6.3).⁵¹

Statistical analysis as described in the SAP (Statistical Analysis Plan) will be done after database lock and authorization of data release according to standard operating procedures.⁵²

Unblinding by drug safety personnel of the sponsor

For regulatory reporting purposes, drug safety personnel of the sponsor are permitted to unblind individual cases.

In compliance with applicable regulations, in the event of a suspected unexpected serious adverse reaction (SUSAR) (see Section 7.5.1.5), the patient's treatment code will usually be unblinded before reporting to the health authorities, Independent Ethics Committees (IECs)/ Institutional Review Boards (IRBs), and investigators (see Section 7.5.1.4) if the SUSAR was related to the blinded treatment.

⁵⁰ Per Amendment 4

⁵¹ Per Amendment 5

⁵² Per Amendment 5

Emergency unblinding by the investigator

In case of emergency, investigators are permitted to unblind individual cases via the IxRS. However, investigators are obligated to restrict such unblinding to cases of emergency where the unblinding result is of importance for the acute treatment strategy.

Investigators should note that the occurrence of a serious adverse event (SAE) should not routinely precipitate the immediate unblinding of the label.

Date, time, and reason for unblinding must be captured in the relevant eCRF. Please refer to the IxRS and eCRF completion guideline for instructions.

Any patient who discontinues study medication will remain under medical supervision until discharge or transfer is medically acceptable. Patients who withdraw from the study or discontinue study medication should take part at the termination visit (refer to Section 7.1.2.8) and the safety follow-up visit (refer to Section 7.1.2.9)⁵³. Further therapy is at the discretion of the investigational site.

Unblinding for ongoing safety monitoring

In order to allow ongoing safety monitoring during the conduct of the study by an external DMC, members of the committee will receive unblinded safety data. The involvement of an external statistical analysis center in this process will ensure that unblinded information is not available for third parties. Details of the process are described in the DMC charter.

6.6 Drug logistics and accountability

All study drugs will be stored at the investigational site in accordance with Good Clinical Practice (GCP) and GMP requirements and the instructions given by the clinical supplies department of the sponsor, and will be inaccessible to unauthorized personnel. Special storage conditions and a complete record of batch numbers and expiry dates can be found in the sponsor study file; the site-relevant elements of this information will be available in the investigator site file. The responsible site personnel will confirm receipt of study drug via IxRS and will use the study drug only within the framework of this clinical study and in accordance with this protocol. Receipt, distribution, return and destruction (if any) of the study drug must be properly documented according to the sponsor's agreed and specified procedures.

Written instructions on medication destruction will be made available to affected parties as applicable.

6.7 Treatment compliance

A drug dispensing log will be completed for each patient. The overall compliance with study drug intake should be between 80% and 120% of the calculated dose. The date of dispensing the study drug to the patient will be documented.

Patients will receive study medication dispensed per visit schedule (see Section 7.1.1).

To record treatment compliance, patients will be instructed to bring all study drug packaging, including unused study drug and empty packaging, to the investigative site at each study visit. Tablets will be counted for a compliance check.

⁵³ Per Amendment 4

If a dose of study drug is missed, the patient should take a dose immediately and continue with the TID intake as recommended on the following day. The dose should not be doubled to make up for a missed dose within the same day.

